9.1.2 Measurement of primary results

The primary measurements refer to the area of application, lumbar back area, right-sided or left-sided paravertebral depending on randomization.

Perfusion of skin microcirculation

The perfusion of the skin microcirculation is visualized using the Laser Speckle Contrast Imager (moorFLPI 2, moor instruments, www.moor.co.uk). This measurement is non-invasive. The "moorFLPI-2 Full-Field Laser Perfusion Imager" measures blood flow measured in flow rates (arbitrary units) of the skin's microcirculation. The laser is intended for clinical and physiological research. The fabric is illuminated with a divergent infrared laser beam. The laser measures down to a depth of 1mm, so it mainly detects the superficial blood flow, speed and concentration of red blood cells. This measurement is measured during the baseline measurements, after the step-up task and up to 30 min after the cold water bath of the hand (5 min interval).

Oxygen saturation of the muscles and brain

The oxygen saturation of the muscles and brain is measured non-invasively with a deep tissue oxygenation monitor (moorVMS-NIRS, moor instruments, www.moor.co.uk). For this purpose, adhesive electrodes are attached over the muscle and forehead. This measurement is measured during the baseline measurements, after the step-up task and up to 30 min after the cold water bath of the hand (5 min interval).

Oxygen saturation of the blood

The oxygen saturation of the blood is measured with a portable pulse oximeter with finger clip probe (Nonin 7500, Nonin medical B.V., Plymouth, USA). This measurement is measured during the baseline measurements, after the step-up task and up to 30 min after the cold water bath of the hand (5 min interval).

Blood pressure and heart rate

The heart rate is measured with a heart rate belt and an additional 2-point ECG (Actiheart, Camntech Ltd., Cambridge, UK). Blood pressure is measured by means of an electronically automated upper arm blood pressure monitor (Boso-Medicus uno). This measurement is measured during the baseline measurements, after the step-up task and up to 30 min after the cold water bath of the hand (5 min interval).

Skin temperature

Skin temperature is measured via the iButton system (www.ibuttonlink.com). The self-adhesive sensors transmit the information about the skin temperature wirelessly to a computer. Furthermore, the skin temperature is recorded by means of a thermal imaging camera (FLIR). This measurement is measured during the baseline measurements, after the step-up task and up to 30 min after the cold water bath of the hand (5 min interval).

Lactate and creatine kinase

SUPSI

The lactate and creatine kinase are carried out by capillary blood measurement (Accutrend, Roche Diagnostic, Rotkreuz, Switzerland & Reflotron, Roche Diagnostic, Rotkreuz, Switzerland). The affected area is disinfected and a superficial wound is pierced to take capillary blood. This measurement is measured during the baseline measurements, after the step-up task and up to 30 min after the cold water bath of the hand (5 min interval).

Balance measurement

The fluctuations of the hull are recorded and evaluated with the Sway Star™ System (www.b2i.info). The Sway Star™ is a measuring instrument that contains gyroscopes. It is attached to a belt that is placed around the patient's waist. The data is evaluated with the associated Sway Star™ software and transferred to the data sheet. This measurement is carried out after the baseline measurement and after the cold water bath immersion of the hand.

Pain sensation

The pain threshold is measured using a pain pressure algometer (NOD, www.to-nod.com). As soon as the patient reports pain, this measurement is stopped. This measurement is carried out after the baseline measurement and after the cold water bath immersion of the hand.

Psychological measurements

The psychological measurements (sleep disorder, altitude sickness, dyspnea, state of mind, drowsiness) are evaluated on the basis of written questionnaires.

The cognitive test battery consists of 8 tasks (ANAM, US Department of Defence, Vista Life Sciences, USA), which are carried out on a laptop computer.

These measurements are carried out after the baseline measurement and after the cold water bath immersion of the hand.

9.1.3 Measurement of secondary results

The secondary measurement of thermal comfort and temperature perception can be measured within 1 min.

Thermal comfort and temperature perception

This parameter is measured using a scale. The test subjects indicate their subjective temperature perception on a 9-point scale from -4 (very cold) to +4 (very hot). They then rate the thermal comfort between 0 (pleasant) and 4 (extremely unpleasant) on a 5-point scale. These measurements are carried out after the baseline measurement and after the cold water bath immersion of the hand.

9.1.4 Collection of further results

No further results will be collected.

9.1.5 Collection of safety parameters

Apart from the health questionnaire (including pregnancy test for female subjects), no safety parameters are collected.

SUPSI

9.1.5.1 Unfavorable events

In the event of an allergic reaction, the experiment is stopped immediately.

9.1.5.2 Laboratory parameters

-

9.1.5.3 Vital signs

-

9.1.6 Collection of data in case of early termination of studies

For the participants, there is no disadvantage in the event of an (arbitrary) discontinuation of study participation and no further interventions are necessary for follow-up treatment. The data collected to date will be evaluated as far as possible and included in the data analysis (in accordance with Art. 9 ClinO).

However, if study participation was discontinued due to a reaction occurring during study participation, this will be recorded and reported to the sponsor investigator (head of the research laboratory), study management and supervisor of the study. In the event of necessary medical treatment, the report is sent to the business liability insurance of Thim van der Laan AG (Basler Versicherung).

The following are recorded:

- Date and time of the incident
- Course of the incident
- Persons involved & witnesses
- Study ID (specified by the CEC)
- Personal data of the person concerned (if not previously recorded)

9.2 Procedure at each visit of the test subjects

9.2.1 Single measurement

The project involves multiple visits.

9.2.2 Multiple visits

After contact has been made by telephone and suitability has been determined by telephone, the subject information and the declaration of consent are submitted for inspection and reading. If the subject agrees with the study conditions and criteria, he or she registers to make an appointment for the 1st contact day.

The 1st contact day includes, in the order described, the; On-site explanations, signing the consent form, completing the health questionnaire and taking the pregnancy test for female subjects. If these points are passed positively, an appointment is made for the actual measurement day (2nd-5th contact day).

1. On-site explanation and completion of the health questionnaire, 1st contact day

The subjects will be comprehensively informed about the process and possible risks before they are confirmed to participate in the study. The declaration of consent explains to them what their rights and obligations are when participating and that they may withdraw from participation at any time without giving reasons, without incurring any disadvantages as a result. More detailed information can be found in chapter 2.7. In addition, a health questionnaire is filled out to identify any risks. An initial selection

SUPSI

process of suitable test persons takes place. If the health form has been completed and no risks have been identified, the test subjects are summoned to the 2nd day of contact.

2. Measurement, 2nd-5th day of contact

2.1 Preparation of the subject

The subject lies in his underwear on a treatment table for a period of 20 minutes. This is followed by the baseline measurement.

2.2 Intervention

The subject is then exposed to either the simulated altitude or the normobaric & normoxic situation. Afterwards, a step-up task of 5 minutes and a cold water bath immersion of the hand for 5 minutes is performed. In the terrestrial situation, the subject is measured at the time of arrival at the SAC Hut, as well as the following day after an overnight stay at the SAC Hut. The experimental procedure is therefore illustrated:

[figure not shown]

Illustration of the experimental process

2.3 Follow-up measurement

After the step-up task and after the cold water bath immersion of the hand, follow-up measurements are carried out.

After the step-up task, the perfusion of the microcirculation, the oxygen saturation of the muscles, the brain, the blood, the blood pressure and the heart rate, the skin temperature, the lactate and the creatine kinase are measured again once.

After cold water immersion, these parameters are measured again at intervals of 5 min up to 30 min after hand immersion. After these parameters have been collected, the balance measurement, the pain sensation as well as the psychological measurements and the thermal comfort and temperature

SUPSI

perception are measured again.

After this measurement day is completed, the test subjects either return to the laboratory and carry out the same test procedure in the mountain restaurant in Valais.

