
Measurements and procedures:
	
During the 20-minute acclimatization phase, the application areas are drawn (skin-friendly pen) and the appliances are attached. If necessary, the hypoxia mask is then put on, the treatment is started and the baseline measurements are carried out. After the baseline measurement, the 5-minute step-up task is performed. After this task, the physiological parameters are measured again. These measurements were followed by a 5-minute cold water bath of the hand. Afterwards, the physiological measurements are carried out up to 30 minutes after the cold water bath (5 min interval) and the questionnaires are filled out afterwards. In the terrestrial altitude situation, the test subject spends the night in the Hohsaas mountain restaurant (https://www.hohsaas-bergrestaurant.ch, canton of Valais) and the measurements are repeated the next day.
 
Perfusion of skin microcirculation
 
The perfusion of the skin microcirculation is visualized using the Laser Speckle Contrast Imager (moorFLPI 2, moor instruments, www.moor.co.uk). This measurement is measured during the baseline measurements, after the step-up task and up to 30 min after the cold water bath of the hand (5 min interval).
 
Oxygen saturation of the muscles and brain
 
The oxygen saturation of the muscles and brain is measured non-invasively with a deep tissue oxygenation monitor (moorVMS-NIRS, moor instruments, www.moor.co.uk). For this purpose, adhesive electrodes are attached over the muscle and forehead. This measurement is measured during the baseline measurements, after the step-up task and up to 30 min after the cold water bath of the hand (5 min interval).
 
Oxygen saturation of the blood
 
The oxygen saturation of the blood is measured with a portable pulse oximeter with finger clip probe (Nonin 7500, Nonin medical B.V., Plymouth, USA). This measurement is measured during the baseline measurements, after the step-up task and up to 30 min after the cold water bath of the hand (5 min interval).
 
Blood pressure and heart rate
 
The heart rate is measured with a heart rate belt and an additional 2-point ECG (Actiheart, Camntech Ltd., Cambridge, UK). Blood pressure is determined by means of an electronically automated upper arm blood pressure meter (Boso-Medicus uno). This measurement is measured during the baseline measurements, after the step-up task and up to 30 min after the cold water bath of the hand (5 min interval).
 
Skin temperature
 
Skin temperature is measured via the iButton system (www.ibuttonlink.com). The self-adhesive sensors transmit the information about the skin temperature wirelessly to a computer. Furthermore, the skin temperature is recorded by means of a thermal imaging camera (FLIR). This measurement is measured during the baseline measurements, after the step-up task and up to 30 min after the cold water bath of the hand (5 min interval).

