5.2 Secondary outcomes

Thermal comfort and temperature perception

This parameter is measured using a scale. The test subjects indicate their subjective temperature perception on a 9-point scale from -4 (very cold) to +4 (very hot). They then rate the thermal comfort between 0 (pleasant) and 4 (extremely unpleasant) on a 5-point scale. These measurements are carried out after the baseline measurement and after the cold water bath immersion of the hand.

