11.4.2 Primary Analysis

The statistical data analysis will be carried out by [name]. [name] after completion of the data collection of the entire project.

Repeated measures analysis of variance (MANOVA)

2 factors:

Factor 1: Situation (simulated altitude vs. terrestrial altitude)

Factor 2: Time (baseline, after step-up task, 0, 5, 10, 15, 20, 25, 30 min post-cold water immersion of the hand)

Repeated measures analysis of variance (MANOVA)

2 factors:

Factor 1: Situation (simulated altitude vs. terrestrial altitude)

Factor 2: Time (baseline, post-cold water immersion of the hand)

The significance level is set at $P < 0.05$, and the statistical data analysis is carried out with SPSS V. 23.

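### The two thermal scales are re-read only 30 minutes or more after a 5-minute hand immersion, yet are analysed as the post-immersion level

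*Combined protocol and SAP*

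**What the plan says.** The stimulus is brief. Under 9.2.2 (2.2 Intervention), "a step-up task of 5 minutes and a cold water bath immersion of the hand for 5 minutes is performed".

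The order afterwards is explicit in 2.3 Follow-up measurement of the same section. For the physiological set: "After cold water immersion, these parameters are measured again at intervals of 5 min up to 30 min after hand immersion". For the rest: "After these parameters have been collected, the balance measurement, the pain sensation as well as the psychological measurements and the thermal comfort" and temperature perception follow. The synopsis (Measurements and procedures) gives the same order for the questionnaires: "the physiological measurements are carried out up to 30 minutes after the cold water bath (5 min interval) and the questionnaires are filled out afterwards".

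The outcome definition for thermal comfort and temperature perception in 5.2, repeated in 9.1.3, names two readings and no minute: "These measurements are carried out after the baseline measurement and after the cold water bath immersion of the hand". Section 9.1.3 adds: "The secondary measurement of thermal comfort and temperature perception can be measured within 1 min". Section 12.2.1 says the two scales are asked orally.

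Section 11.4.2 has two time structures. One has a level at baseline, one after the step-up task, and one every 5 minutes from 0 to 30 after immersion. The other has two levels: "Factor 2: Time (baseline, post-cold water immersion of the hand". The synopsis assigns the psychological parameters, balance, thermal comfort and temperature perception to the two-level version. It does not name pain there, but pain also has only two readings, so no other planned structure fits it.

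**The concern.** Section 4.1 sets out to study changes after the step-up task and after the 5-minute cold-water immersion. Thermal comfort and temperature perception are the only secondary outcomes (4.3, 5.2). They are also the ratings a reader would most naturally take as the participant's response to the cold. Their only reading after the stimulus comes once the whole recovery series is finished, and the analysis label does not show this. The physiological outcomes, by contrast, are read from 0 minutes on, so the plan itself allows for a response that changes over that half hour.

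At stake is how a null result is read. With one late reading, the data cannot separate two explanations: that the immediate response to cold did not differ between situations, or that it differed and had faded by the time it was rated. No analysis can recover a reading that was not taken.

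**Working it through.** **1. The plan's own timetable.** The blocks in 9.1 are baseline 20, step-up task 5, follow-up 10, immersion 5 and follow-up 40 minutes. Their sum is 20 + 5 + 10 + 5 + 40 = 80 minutes, within the stated maximum of 90. The total commitment also reproduces: 30 + 4 × 110 = 470 minutes.

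**2. When the late readings fall.** Count from the end of immersion.
- The physiological series occupies 0 to 30 minutes, so the earliest possible reading of any later measure is at 30 minutes. That is 30 / 5 = 6 times the length of the stimulus.
- The listed order is balance, pain, psychological measures, then the thermal scales. Section 9.1.1 allows up to 10 minutes for the questionnaires, which puts the thermal scales at about 30 + 10 = 40 minutes. This agrees with the 40-minute follow-up block.
- Any further time for balance, pain and the cognitive battery moves the thermal scales later still.

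**3. Is an earlier reading scheduled anywhere?** The synopsis, 5.1, 5.2, 9.1.2 and 9.1.3 say only that these measures are repeated after the immersion. That is compatible with the order in 2.3 and adds no earlier time. The table in 9.1 lists everything in one block without times. So no reading of these measures is planned during immersion or in the first 30 minutes after it.

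**4. How much of an immediate effect could remain.** The documents give no water temperature and no recovery rate, so the following is an assumption shown as a range. With exponential recovery, the share left at time t is 2^(−t / half-time).

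| Assumed half-time | Left at 30 min | Left at 40 min |
|---|---|---|
| 5 min | 2^(−6) = 1.6% | 2^(−8) = 0.4% |
| 10 min | 2^(−3) = 12.5% | 2^(−4) = 6.3% |
| 15 min | 2^(−2) = 25% | 2^(−2.67) = 15.7% |
| 30 min | 2^(−1) = 50% | 2^(−1.33) = 39.7% |

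For illustration only, an assumed 3-point shift at 0 minutes on the 9-point temperature scale would read 3 × 0.016 = 0.05 to 3 × 0.50 = 1.5 points at 30 minutes. The conclusion does not depend on any one row. What matters is that the late reading cannot show which row applies.

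The sample-size calculation in 11.2 is not affected by this point.

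**The case against.** The strongest reply is that the plan's question is about altitude, not cold. The hypothesis in 11.1 contrasts simulated with terrestrial altitude for thermal comfort and temperature perception and does not mention an acute cold response. A late reading can still show a difference between situations. The baseline reading can contribute too: at the hut it is taken at altitude, and in the synopsis the mask goes on before baseline, although 9.2.2 reads otherwise. The label is also literally true. All this stands, and it limits the point: the altitude comparison is not invalidated. It does not remove the point, because the stated aim names the immersion and nothing tells a reader that the level means late recovery.

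A reader might infer four stronger things that the documents do not support.
- *That participants have rewarmed when they are rated.* No water temperature or recovery rate is given. The supportable statement is that they are at least 30 minutes into recovery.
- *That only a negligible effect can remain.* Any low ceiling comes from choosing short half-times. At 30 minutes' half-time, half the effect is left.
- *That the secondary outcome rests on the late reading alone.* There is also a baseline reading. What is missing is any other reading after the stimulus.
- *That the pain threshold loses a local cold effect and should be moved to 0 minutes.* Section 9.1.2 places the primary measurements at the lumbar back, which was not cooled, so at most an immediate systemic response is missed. Algometry at 0 minutes would also delay or disturb the 0-minute perfusion, heart-rate and blood-pressure readings, which are primary outcomes. That slot is already tight: 9.1.1 allows up to 10 minutes for the primary set, against 5-minute intervals. Moving pain is a trade-off, not a plain improvement.

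**Conclusion.** The point holds for timing and labelling. The order in 2.3 puts the only post-stimulus reading of thermal comfort and temperature perception at least 30 minutes, and by the listed order about 40 minutes, after a 5-minute immersion, and 11.4.2 analyses it simply as the level after immersion. Balance, pain, the questionnaires and the cognitive battery share the delay. The physiological outcomes do not, since they have a 0-minute reading.

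The share of an immediate response left at 30 minutes is unknown. Under exponential recovery with assumed half-times of 5 to 30 minutes it would be about 2% to 50%. A null result on the thermal scales would therefore be informative about late recovery and uninformative about the immediate response to cold. The timing is certain from the text; the size of the loss rests wholly on the assumed recovery rate.

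**What to change.** - In 2.3 (under 9.2.2) and 9.1.3, add the two oral thermal scales at 0 minutes after immersion, asked alongside the 0-minute physiological readings. Keep the existing late reading.
- In 11.4.2, analyse time for thermal comfort and temperature perception as baseline, 0 minutes and recovery (at least 30 minutes).
- For pain, balance, the questionnaires and cognition, leave the order unchanged, label the second level as at least 30 minutes after immersion, and limit conclusions to late recovery. State explicitly that pain belongs to the two-level analysis.

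The cost is about 1 extra minute per session, or about 4 minutes per participant over the four sessions (simulated, terrestrial twice, control). The 80 minutes of scheduled blocks leave room for this within the 90-minute maximum. The secondary analysis gains one time level. No equipment or visit is added. The reading has to be added before data are collected; after that, only the relabelling and the narrower conclusions remain possible.

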2.4 Conclusion and compensation

After the last follow-up measurement and after the subject has gone through all situations, the examination is over for the subject. He/she will receive the amount due to him/her according to the advertisement. The lump sum is 100 CHF. The gondola ride, the overnight stay, the travel costs to Valais and the meals in the SAC hut are covered by the University of Applied Sciences and Arts Southern Switzerland. The total compensation is not dependent on the completion of the study. The test subjects will be reimbursed for the costs in any case.

SUPSI

10 SAFETY

Other clinical trial with a medical device in the risk category Cat. **A** KlinV (Art. 20)

No medication will be administered to the subjects, nor will tissue samples be taken. No invasive methods are used.

No further security aspects are expected.

10.1 Drug study

10.1.1 Definition and assessment of (serious) adverse events and other safety related events

-

10.1.2 Reporting of serious adverse events (SAE) and other safety related events

-

10.1.3 Follow up of (Serious) Adverse Events

-

10.2 Medical Device Category C studies

-

10.2.1 Definition and Assessment of (Serious) Adverse Events and other safety related events

-

10.2.2 Reporting of (Serious) Adverse Events and other safety related events

-

10.2.3 Follow up of (Serious) Adverse Events

-

10.3 Medical Device Category A studies

This project is carried out with a CE certified product. It is a study with 24 or fewer subjects. The study aims to gain fundamental knowledge in the field of altitude training. The study focuses on basic findings. The monitoring for quality assurance is carried out by [name], who has gained numerous experiences and published studies in the field of extreme environmental conditions. In addition, a doctor is present during the measurements.

